## Other criteria for hemolysis:

- If the Direct Coombs' Test is negative, but other hemolysis tests are indicative of hemolysis, the Investigator should conduct further tests to confirm hemolysis as clinically indicated and at the discretion of the Investigator. This may include repeat Direct Coombs' Test, haptoglobin, serum LDH, plasma free hemoglobin, bilirubin and urine hemosiderin.
- A drop in hemoglobin of 2 g/dL or greater, in conjunction with both a drop in serum haptoglobin to below the lower limit of normal and a rise in serum LDH from baseline, would suggest intravascular hemolysis:
  - Investigator should review all results with reference to above criteria, and in conjunction with patient medical history to determine if there is clinically significant hemolysis. Investigator should conduct further tests as clinically indicated and at the discretion of the Investigator. This may include repeat Direct Coombs' Test, haptoglobin, serum LDH, plasma free hemoglobin, bilirubin and urine hemosiderin.
- Clinically significant hemolysis should be diagnosed taking into account the above criteria (drop in hemoglobin of 2 g/dL or greater, in conjunction with both a drop in serum haptoglobin to below the lower limit of normal and a rise in serum LDH from baseline) and any additional tests, as applicable.
- Clinically significant hemolysis will be reported as an adverse event. Subjects with clinically significant hemolysis should have a Direct Coombs' test and other tests for hemolysis (as detailed above) before every subsequent infusion at the clinic.

# 7.4.3. Virology Testing

If the tests for HBV, HCV, HIV, or Parvovirus B19 suggest a change in viral status of the subject, the tests will be repeated by the central laboratory. If a change in viral status is confirmed by a second independent test, the reserve sample taken before the first infusion of Subgam-VF will be retested in the same laboratory in the same batch as a retest of the suspect

Page 27 of 87

sample. The central laboratory will inform the Sponsor and the designated CRO within one business day of a confirmed report of a change in viral status.

# 7.4.4. Reserve Samples

Reserve plasma and serum samples will be collected at all relevant time points, for reanalysis if needed, e.g. if an original sample is spoiled or if results are discrepant. Where necessary an additional blood sample will be collected; at other time points plasma or serum aliquots will be split so that a reserve plasma or serum sample can be retained at site. See Appendix IV and Laboratory Manual.

Reserve samples should be sent to the central laboratory within one month of collection where they will be stored at -70°C for the duration of the study. Reserve samples may be kept until the licence for Subgam-VF is granted by the relevant regulatory authorities and will be used, if required, for repeat assays at the request of a regulatory agency. For full details, please see separate Laboratory Manual.

Table 4 (Appendix V) displays the suggested maximum blood withdrawal for children. If the volume of blood withdrawn within 30 days is expected to exceed that specified on Table 4, then the Sponsor/Contract Research Organization (CRO) should be contacted to discuss order of priority for blood sampling. In these cases it will likely be the reserve samples that will not be taken so as to not exceed the maximum blood volumes allowed. The deviation must be documented appropriately on the eCRF.

# 7.4.5. Archive Sample

A blood sample will be collected from each subject immediately before the first infusion of Subgam-VF and at the follow-up (week 27) visit before another IgG product is given and sent at the end of the study (after all subjects have completed) to the central laboratory for onward dispatch to Cryo-store for long-term storage. Serum will be stored in tubes at -70°C for a minimum of 15 years after the trial is complete. Samples will be used for serology and NAT testing if required in the future. The handling and shipping of these samples will be coordinated by the central laboratory.

## 7.5. Informed Consent

Written informed consent (and assent when appropriate) must be obtained from the subject and where appropriate by the subject's parent/legal guardian and signed by a suitable qualified and trained person, first in the protocol and the legal and ethical requirements of the study, before any study procedures are carried out (see Appendix II, Section 2).

# 7.6. Medical History

A complete medical history of the subject including demographics will be taken at Screening and an interval medical history (adverse events) will be taken at subsequent clinic visits.

Page 28 of 87

Special attention should be paid to any aspect of the medical history or any clinical/laboratory feature that may serve to exclude the subject from participation.

Chronic infections and conditions that may require intermittent or continuous treatment during the study and/or could potentially change in frequency or severity during the study such as: cough, chronic bronchitis, chronic sinusitis, and arthritis and the type and frequency of treatment required should also be assessed and recorded so that symptoms of these conditions can be distinguished from treatment emergent adverse events (TEAEs) as the study progresses.

Any elective procedures that are planned for pre-existing conditions should be recorded.

Previous immunologic data that document the specific immunologic diagnosis will be recorded.

The medical history must include the use of prior IGIV and SCIG treatments received and how they were tolerated if available. The previous use of an IGIV and SCIG product must be documented in the subject's eCRF.

# 7.7. Physical Examination

Physical examination will be performed by an appropriately qualified member of staff at the study site. The physical examination is also a safety variable.

Elements of the examination should include:

- General appearance
- Head, eyes, ears, nose, throat
- Cardiovascular
- Respiratory
- Skin

Other body systems examined should be specified in the eCRF.

Height will be measured at screening and weight will be measured at screening and at every clinic visit.

Any clinically significant change from baseline in any system will be recorded as an AE (Appendix I).

# 7.8. Monitoring for thromboembolic events (TEE)

Monitoring for thromboembolic events (TEE) will be performed at screening (baseline) and at the Week 27 follow up visit (as well as when clinically indicated); this will include assessment of lower extremities for pain, swelling, tenderness or redness, also a respiratory

Page 29 of 87

examination for any sudden onset of shortness of breath and any associated signs or symptoms of pulmonary embolus.

Assessment is particularly important in patients at high risk of TEE including prolonged immobilization, hypercoagulable conditions, history of venous or arterial thrombosis, use of estrogens, indwelling central vascular catheters, hyperviscosity and cardiovascular risk factors.

Subjects will be educated about the risk of TEE events and the signs and symptoms that they should look out for. This information will be included in the written instructions for home infusions. Subjects will be instructed to contact the site immediately should they experience any symptoms of concern.

Any clinically significant change from baseline in any system will be recorded as an AE (see Appendix I).

#### 7.9. Concomitant Medication

All concomitant prescription and non-prescription medications received by the subject should be documented in the source notes, eCRF and study diary (when away from the site).

The following concomitant medications are excluded during the study:

- Steroids (long term daily,  $\geq 0.15$  mg of prednisone equivalent/kg/day). Requirement for short or intermittent courses of steroids would not exclude a subject.
- Immunosuppressive drugs.
- Immunomodulatory drugs.
- Vaccination with live attenuated virus vaccines during the trial (ie. until final follow up visit).

# 7.10. Chest X-Ray

A baseline chest X-ray (posterior-anterior and lateral) will be obtained on all subjects unless a chest X-ray taken within the previous 12 months is available to be used as a baseline.

## 7.11. Vital Signs

Vital signs assessed by qualified personnel will be entered on the eCRF. The vital signs to be observed will be:

- diastolic blood pressure (mmHg)
- systolic blood pressure (mmHg)
- pulse rate (beats/min)
- respiration rate (breaths/min)
- temperature (°C)

## Page 30 of 87

The subject must be in the same position each time vital signs are obtained. Temperature must be recorded using the same method every time e.g. orally, under the arm or via another common method.

Any clinically significant changes in vital signs will be reported as AEs as described in Section 10.2.

Clinically significant hypotension and/or anaphylactic reactions (significant hypotension with generalized hives/angioedema or bronchospasm) warrant discontinuation of the infusion and administration of appropriate supportive care as deemed necessary by the investigator (this may include: epinephrine, antihistamine, corticosteroids, supplemental oxygen, expansion of the plasma volume as necessary, etc.). These occurrences must be recorded on the eCRF as AEs. At the discretion of the investigator, the subject may be withdrawn from the study, but will complete the follow-up visits.

If a subject has been assessed as being dehydrated and is given intravenous fluids before beginning the subcutaneous study infusion, the baseline vital signs will be taken after the rehydration fluids have been given but before infusion of investigational product.

Vital signs will be recorded once during the screening and follow up visits.

Vital signs will be recorded during site visits at the following times:

- 10 minutes before the start of each Subgam-VF infusion (+/- 5 minutes)
- 30 minutes after stopping the Subgam-VF infusion (+/- 15 minutes)

Vital signs are also an important safety variable.

If any AE of moderate or severe intensity occurs, the rate of the infusion at which this AE occurred will be recorded, and the infusion rate will be reduced appropriately, depending upon the severity of the AE symptoms. The infusion may then be resumed at a rate tolerated by the subject. Also see the most current Subgam-VF Investigator Brochure (IB) for a list of common product-related AEs.

Before listing changes in vital signs as AEs, each change should be assessed for clinical relevance.

## 7.12. IgG - Blood Levels of the Previous IgG Preparation

As screening is likely to be performed during the same visit where the subject will receive their regularly scheduled infusion of a licensed (or investigational stage III, IIIb) IGIV or SCIG), the sample to determine trough IgG levels must be drawn before the infusion is started. Trough IgG levels must be documented to demonstrate that the subject is in a steady state. The minimum target trough level of IgG is 600 mg/dL. In addition, the dose, treatment interval, method of administration (IV/SC) and trade name or investigational reference of their current preparation must be recorded.

Page 31 of 87

Samples will also be collected as per the Schedule of Assessments (Appendix IV, Table 2), and should always be taken before administration of the product.

# 7.13. IgG Subclasses-Blood Levels of the Previous IgG Preparation

Samples will also be collected as per the Schedule of Assessments (Appendix IV, Table 2) to determine the survival of the IgG subclasses during treatment with Subgam-VF. Samples should always be taken before administration of the product.

# 7.14. Specific Antibody Function

A sample will be taken prior to certain infusions (see Appendix IV, Table 2) to test for antibodies against the following antigens:

- Haemophilus influenzae B (screening and follow up [Week27])
- Streptococcus pneumoniae (screening and follow up [Week27])
- *Measles* (follow up [Week27])

# 7.15. IgA and IgM Levels

If levels of IgA and IgM in serum measured within the previous 12 months are not available, blood samples for IgA and IgM levels will be obtained. Samples should be taken at screening only.

# 7.16. Routine Pre-medications

Routine premedication to reduce potential adverse effects associated with the SCIG infusion are discouraged. Exceptions:

- Premedication will be permitted if a subject has reported systemic adverse events on two Subgam-VF infusions.
- If required, local anesthesia (for example Emla cream) is also allowed before any infusion to reduce the pain associated with needle insertion.

The routine long-term use of corticosteroids is not allowed. Oral and parenteral steroids are allowed if the average daily dose is < 0.15 mg prednisone equivalent/kg/day. Short or intermittent courses of > 0.15 mg/kg/day are allowed if required.

If a subject who previously required premedication before infusion with a licensed or experimental (Phase III or IIIb) IgG product is enrolled, their previous use of premedication, as well as associated side-effects must be recorded on the eCRF.

# 7.17. Data Recording

All data from the study collected at site will be entered into the eCRF. Subjects will record the data listed in 7.18 directly into the study diary, which will be reviewed by the study site at each visit. All key data must be entered into the subjects' medical record before they are entered into the eCRF (also see Appendix II, section 12.4). Subject diary data will not be transcribed but will be used as source data for home infusions, adverse events and concomitant medication.

# 7.18. Subject Study Diary

The subject or parent/guardian will complete a study diary daily between visits, starting after the Screening Visit. The data from the study diary will be reviewed at each site visit by qualified site personnel. The data to be recorded in the study diary are as follows:

- AEs (including time [24 hour clock] and date of onset/stop date and any AEs following infusion site inspection).
- Concomitant medication, especially antibiotics
- Subgam-VF infusion details including:
  - o Batch number
  - o Date of infusion
  - Start and stop times of the infusion
  - Volume of Subgam-VF infused and number of vials used
  - Infusion rate
  - o Infusion sites used and any associated infusion site reactions.

For children and adolescents the parent/legal guardian is required to oversee that the diary is completed accurately and legibly.

The study staff will review the data from the subject study diary at each visit, to ensure the diary is completed correctly. If there is any discrepancies or missing data this will be discussed with the subject and then if required corrected by the subject. These discussions will be documented in the subject's medical notes.

# 7.19. Subject Withdrawal

If more than five subjects withdraw prematurely from the study then a sufficient number of subjects will be replaced to ensure data for 30 evaluable subjects.

Subjects can be withdrawn from the study for any of the following reasons:

• The subject or parent/legal guardian withdraws consent for the study.

- The subject or parent/legal guardian is uncooperative and non-compliant (defined as the subject missing two consecutive or three overall study visits) with respect to provisions of the protocol.
- The subject misses two scheduled infusions
- The subject has a serious AE (SAE) while participating in the study and, at the discretion of the site investigator, is withdrawn.
- The subject becomes pregnant while participating in the study (the pregnancy will not be recorded as an SAE, but will be captured on a Pregnancy Report Form and followed through until delivery or elective/spontaneous termination).
- The subject requires treatment with any of the medications listed in the exclusion criteria.

Investigators may withdraw subjects at any time if they feel it is not in the subject's best interests to continue. Reasonable efforts will be made to contact the parent/legal guardian and subject. If the subject is lost to follow-up, this will be documented in the subject's medical records.

In exceptional circumstances relating to safety, the sponsor may withdraw subjects at any time.

Data and samples collected up until a subject's withdrawal from the study will be used in the analysis. Subjects who have completed the study and subjects who have withdrawn cannot participate in the study for a second time.

# 7.19.1. Evaluations at Early Withdrawal

If a subject withdraws from the study or is dropped from the study for any reason, all tests identified for the end of study follow-up visit will be performed. If subjects have stopped Subgam-VF treatment and started another product, this will be taken into consideration in the analysis of the data.

# 7.20. Study Termination

Conditions for early termination are detailed in Appendix II, section 8.

#### 8. DESCRIPTION OF TREATMENT ADMINISTERED

## 8.1. Investigational Product

#### 8.1.1. Identification and Batch Numbers

It is planned to use one batch of Subgam-VF in this study. Additional batches may be used if required. The batch number(s) of Subgam-VF will be documented in the Certificate of Analysis that will be filed in the Trial Master File. The actual batch number will be

Page 34 of 87

documented in the eCRF for each infusion. A list of all batches used and the subjects who received them will be included in the final study report.

## 8.1.2. Packaging and Labeling

Subgam-VF will be manufactured, packed, and labeled by BPL. The product will be supplied in glass vials (10 mL per vials containing 1600 mg of IgG = 16%) and each vial will be packed in a carton. The vials and the cartons will be labelled with identifying and contact information for BPL. The label will also include the identity, total quantity and volume, concentration, batch number, expiry date, and storage requirements of the product.

# 8.1.3. Conditions for Storage and Use

Subgam-VF should be stored in a refrigerator in a safe area of limited access or a Pharmacy. The product must be protected from light and maintained at a temperature of 36°F to 46°F (2°C to 8°C). Product that has been stored out of a fridge for one period of up to one week at temperatures up to 77°F (25°C) may be returned to the fridge with no change to the expiry date. Subgam-VF must not be frozen (inadvertently or on purpose). A log of daily temperatures in the Pharmacy storage area must be maintained to demonstrate that the product has been stored under the specified conditions.

Once fully trained, subjects will be issued with Subgam-VF for home use. The study staff will ensure that all subjects and parents/guardians are familiar with the correct storage conditions and provided with written storage instructions before any product is dispensed.

# 8.2. Investigational Treatment

# 8.2.1. Dosing Schedule and Rationale

Subgam-VF is a 16% subcutaneous IgG product. The weekly dose of Subgam-VF administered will be calculated by taking the weekly equivalent of the subject's stable IGIV dose, multiplied by 1.37, a dose adjustment coefficient based on other licensed subcutaneous IgG products. If the subject was already receiving a weekly SCIG IgG there will be no dose adjustment. The Subgam-VF dose should remain the same throughout the study, if a subject's weight changes by >5% compared with baseline (screening) or the previous visit, the dose should be adjusted accordingly with the aim of maintaining a stable dose in terms of mg/kg. If the dosage needs to be increased to achieve the required trough IgG level, then this should first be discussed with the CRO Medical Monitor, who will, if needed, discuss with the Sponsor.

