- The subject will return to the clinic every four weeks for a safety assessment (hematology, chemistry, pre and post dose vital signs and physical exam). Their regular Subgam-VF infusion will be given whilst the subject is at the clinic and additional Subgam-VF vials will be dispensed. IgG trough levels will also be measured at the clinic visit every four weeks.
- PK sampling This will occur on Week 21 (defined as Steady State Day 0 to 7), and will continue over the subsequent seven days to allow calculation of AUC (see the PK schedule, Table 3, Appendix IV). If the PK sampling cannot be completed at Week 21 (eg. due to patients work/vacation schedule) then this can be delayed to start at Week 22, 23, 24 or 25; however, the patient should still visit the office/hospital for their week 21 infusion and complete the other assessments scheduled for Visit 8, if possible. Week 22 assessments (Visit 9) will normally coincide with the PK sampling Day 7. However, if PK sampling is delayed, Visit 9 will also be delayed. All PK blood samples will be taken at the study site. However, if an appropriately qualified member of the study team is available, arrangements to collect the remaining PK samples from Steady State Day 1 onwards at the subject's home could be made, to help reduce the number of visits to the sites. Alternatively a Home Health Agency may be utilized to take the PK samples outside of the investigational site.

- In exceptional circumstances, and with prior Sponsor approval, if one of the following PK samples if lost, unevaluable, or not taken it may be taken at the same timepoint during the week following the PK assessment, as long as the same dose in mg/kg has been given:
  - $\circ$  1 day (24 hours  $\pm$  2 hours)
  - $\circ$  2 days (48 hours  $\pm$  4 hours)
  - $\circ$  3 days (72 hours  $\pm$  6 hours)
  - $\circ$  5 days (120 hours  $\pm$  8 hours).

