## Rescheduling of Infusions (visit windows)

If absolutely necessary (e.g. because of unavoidable conflicts) Subgam-VF infusions can be rescheduled +/- 1 days. The reason why this visit was rescheduled should be recorded in the eCRF. If there is a deviation from the scheduled visit/ visit windows, the study monitor should be contacted, and the deviation must be documented appropriately. These circumstances must not become routine. If an infusion is rescheduled the other planned study assessments should also be rescheduled so that these are performed on the day of infusion.

If the infusion just prior to PK sampling has to be rescheduled, then the PK sampling should be postponed to ensure that the PK samples are collected seven days after the last Subgam-VF infusion and the sampling times in Table 3 are adhered to.

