## 11. ASSESSMENT OF PHARMACOKINETICS

# 11.1. Pharmacokinetics of Subgam-VF for Total IgG Levels

All subjects will undergo a PK assessment (see Appendix IV, Table 2 and 3 for the sampling time points).

Where possible, samples from Steady State Day 1 (24 hours after the infusion at Week 21 or if delayed, up to Week 25) onwards may be collected at the subject's home by an appropriately qualified member of the study team. Alternatively a Home Health Agency may be utilized to take the PK samples outside of the investigational site. The subject would be required to sign an IRB/EC approved consent form to permit the site to share the subject's details with the agency in order for them to collect the sample.

The following PK variables for total IgG levels will be determined for the PK population:

- AUC $_{(0-\tau)}$  area under the plasma concentration-time curve of the dosing interval.
- $sAUC_{(0-\tau)}$  area under the plasma concentration-time curve of the dosing interval standardized to one week. This will be calculated for the historical data only.

- Cmax maximum concentration in plasma.
- $t_{max}$  time to reach the maximum concentration in plasma.
- CL– systemic clearance.

The timing of the collection of blood samples for PK should be as per Table 2. The scheduling has been selected to ensure achievement of steady state of Subgam-VF.

A variation of <10% is allowed in the timing for samples as follows:

Steady State Day 1 (24 hours)  $\pm$  2 hours,

Steady State Day 2 (48 hours)  $\pm$  4 hours

Steady State Day 3 (72 hours)  $\pm$  6 hours

Steady State Day 5 (120 hours)  $\pm$  8 hours

Steady State Day 7 (168 hours)  $\pm$  12 hours.

All PK parameters will be calculated based on absolute (uncorrected) and baseline-adjusted (i.e. trough-adjusted at steady state) concentrations.

Details of the PK methods will be outlined in a PK Analysis Plan. The PK Analysis Plan will be finalized before database lock.

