# 13.2.2.1. Subgam PK population

All subjects in the ITT population who have a pre-dose sample at steady state and at least four post-dose samples at steady state, one of them should be the Steady State Day 7 PK sample. In the case of a subject who provides IgG levels at the PK assessment but does not meet the criteria for inclusion in the Subgam PK population, data will be listed only.

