# 13.6.2. Secondary Statistical Analyses

- i. The primary analysis method will be repeated with data derived from baseline-adjusted concentrations.
- ii. A term for dosing interval within treatment will be included in the model described in the primary analysis so that ratios with 90% CI can be presented for Subgam-VF relative to both the 21 day and 28 day dosing interval regimens of Gammaplex.
- iii. The primary analysis model will be extended to include any significant (at the 10% level) covariates or covariate by treatment interactions. Covariates considered for inclusion will include age category, weight, BMI and sex.
- iv. The effect of previous treatment (SCIG or IGIV) on  $AUC_{(0-\tau)}$  in the Subgam PK population will be analysed. If the resulting 90% CI for the ratio lies within the equivalence limit of (0.80, 1.25), it will be concluded that the previous treatment does not affect exposure at steady state. If this is the case then the refined dose adjustment with 90% CI will be presented on the full PK population (in addition to on the PK Dose Adjustment population described below).
- v. In addition, the data from the current study will be restricted to a PK Dose Adjustment population and analysed as per the primary analysis. A refined dose adjustment will be estimated as 1.37/the ratio (Subgam-VF / Gammaplex IGIV) of geometric means for sAUC(0- $\tau$ ) and presented with 90% CI.

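### The refined coefficient divides a fixed 1.37 by the exposure ratio, although the dose may be raised for a low trough; when that happens the coefficient is understated

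*Protocol*

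**What the plan says.** Protocol 8.2.1 sets the starting dose for subjects coming from IGIV at 1.37 times their weekly-equivalent IGIV dose. It then gives a default, "The Subgam-VF dose should remain the same throughout the study", with weight-based adjustment to hold mg/kg stable. The next sentence provides for an exception: "If the dosage needs to be increased to achieve the required trough IgG level", this is first discussed with the CRO medical monitor and, if needed, the sponsor. No limit is given on the size of an increase or on its timing relative to the PK profile.

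Steady state is tied to the schedule. Protocol 7.1 says of the PK sampling: "This will occur on Week 21 (defined as Steady State Day 0 to 7", with a start as late as Week 25 allowed. Protocol 11.1 adds: "The scheduling has been selected to ensure achievement of steady state of Subgam-VF". The Subgam PK population (13.2.2.1) requires "a pre-dose sample at steady state and at least four post-dose samples at steady state", one of which should be Day 7. It has no criterion on dose changes or missed infusions. The PK Dose-Adjustment population (13.2.2.3) removes only subjects previously on weekly SCIG.

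Item v of 13.6.2 then states: "A refined dose adjustment will be estimated as 1.37/the ratio (Subgam-VF / Gammaplex IGIV) of geometric means". The primary conclusion in 13.6.1 is also worded in terms of 1.37.

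There are two safeguards. Section 7.2 postpones the profile in one case: "If the infusion just prior to PK sampling has to be rescheduled". Sections 7.1 and 7.3 require the same mg/kg dose when a lost PK sample is replaced in the following week. On missed infusions, the list of possible withdrawal reasons in 7.19 includes: "The subject misses two scheduled infusions". A single miss has no stated consequence.

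**The concern.** Refining the dose coefficient is a stated secondary objective. The formula in item v is correct only if the previously IGIV-treated subjects were, on average, receiving 1.37 times their IGIV dose when profiled. A trough-driven increase breaks that condition in one direction: the ratio rises because more product was given, while the numerator stays at 1.37. The error does not shrink with more subjects.

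There is a second, smaller issue. The AUC in the PK week reflects the doses of the preceding weeks. A subject whose dose changed, or who missed an infusion, in those weeks enters the analysis labelled as steady state when that is not so. Nothing in the protocol or SAP separates such subjects.

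**Working it through.** **Inputs from the documents.** Factor 1.37; 30 evaluable subjects; SD of log AUC 0.181; 90% CI within 0.80 to 1.25; stated power above 98% at no difference and 86% at a 10% difference (Protocol 13.1, 13.6.1).

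**Assumptions, because the documents give no figure.** IgG half-life of 21, 30 or 40 days; first-order elimination; product-derived IgG only, with AUC proportional to dose; a historical group of 30; and the share of subjects affected and size of increase as shown.

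**1. The plan's own power.** Two one-sided tests on log AUC with 30 against 30 subjects and SD 0.181 give 99.8% at a ratio of 1.00 and 85.5% at 1.10. The normal approximation gives 86.2% at 1.10. The stated figures are reproduced, so this set-up is used in step 4.

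**2. Is the week label reasonable?** Let a = 2^(−7/half-life) be the fraction remaining after one week. After 21 equal weekly doses the level reached is 1 − a^21 = 99%, 97% and 92% of steady state. For constant, uninterrupted dosing, Week 21 is a fair label.

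**3. Effect of increases on item v.** If a share p of subjects is raised by a fraction x and has fully re-equilibrated, the geometric mean factor delivered is 1.37·(1+x)^p, and the ratio is multiplied by the same (1+x)^p. If the true ratio at 1.37 is 1.00, the right coefficient is 1.37 and item v reports 1.37/(1+x)^p.

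| p, x | (1+x)^p | Factor delivered | Item v reports |
|---|---|---|---|
| 10%, 10% | 1.010 | 1.383 | 1.357 |
| 20%, 20% | 1.037 | 1.421 | 1.321 |
| 30%, 30% | 1.082 | 1.482 | 1.266 |

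In the middle row the delivered factor is 3.7% above 1.37. Equivalently, the reported 1.321 is 3.6% below the right value (0.049/1.37). Because the model is additive on the log scale, this correction holds even though only low-trough subjects are raised.

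**4. Effect on the equivalence conclusion (20% raised by 20%).** If the true ratio at 1.37 is 0.80, the chance of declaring equivalence rises from 5.0% to 19.1%. If the true ratio is 1.10, the same increases move it to 1.10 × 1.037 = 1.141 and power falls. By the normal approximation, the standard error is 0.181·√(2/30) = 0.0467 and (ln 1.25 − ln 1.141)/0.0467 − 1.645 = 0.31, so power is about 62% instead of 86%.

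**5. Profiles not at steady state.**
- An infusion missed two weeks before the PK infusion removes (1 − a)·a² of that subject's AUC: 13.0%, 10.8% or 9.0%.
- If 3 of 30 subjects are affected, the geometric mean is multiplied by (1 − loss)^0.1 = 0.986 to 0.991, about 1% lower. Item v then gives 1.389 to 1.383, an error upward.
- A dose raised from Week 17 has had five doses by Week 21 and is 1 − a^5 = 69%, 56% or 46% expressed.

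**6. Which delivered factor to use.** Take a 20% increase from Week 17. The dose at the PK infusion alone credits the full 1.20, while AUC has risen by only 1.137, 1.111 or 1.091; the over-credit is 6%, 8% or 10% for that subject. An average over eight weeks (Weeks 14 to 21) credits 1 + 0.20·5/8 = 1.125, which is within −1% to +3% of the AUC rise. An average over a window is therefore better than a single dose.

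**The case against.** Several points on the other side stand.

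- A reader might infer that 8.2.1 contradicts itself or that dosing is uncontrolled. The text does not support this: constant mg/kg is the rule for every week, and the increase is an exception discussed with the medical monitor.
- A reader might infer that fixing steady state by week is itself a defect. Step 2 shows that it is reasonable for uninterrupted dosing.
- A reader might infer that one missed infusion is expressly permitted. Section 7.19 is only a list of withdrawal reasons, and 7.2 limits rescheduling to one day either way and requires deviations to be documented.
- The number of increases may be small. Entry requires a stable dose and a trough of at least 6 g/L, the same level as the target in 7.12, and former IGIV subjects then receive 1.37 times their dose.
- The primary AUC uses absolute total IgG, so any endogenous IgG shrinks the percentages above.
- The PK Analysis Plan is a separate document that was not available and may contain handling rules.

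These points limit the size but do not remove the gap. The protocol itself fixes the populations and the 1.37/ratio formula, and neither takes account of the factor actually given. The two safeguards do not reach an earlier dose increase or an earlier missed infusion.

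**Conclusion.** The point holds for item v. Whenever trough-driven increases have been made, 1.37/ratio understates the refined coefficient by the proportion in which the delivered factor exceeds 1.37: about 1% to 8% over the assumed scenarios, and nothing if no dose is raised. The half-life matters only for increases not yet fully expressed.

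The steady-state issue is secondary. It is material for an individual profile, but about 1% on the group mean for a few missed infusions, and it moves the coefficient the other way.

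The stronger reading, that the plan makes equivalence at 1.37 easier to conclude, is not supported in general. It is true only if the true ratio at 1.37 is below 1; above 1, the same increases make equivalence harder. Nor do the documents show that the primary comparison as a whole is invalid. The point deserves a change to the analysis text, not to the design.

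**What to change.** 1. **Item v, PK Dose-Adjustment population only.** Replace the constant 1.37 with the geometric mean of each subject's delivered factor: average actual Subgam-VF mg/kg/week over a prespecified window ending with the infusion that starts the profile, divided by the pre-study IGIV dose in mg/kg/week. Count a missed infusion as zero. Report 1.37/ratio alongside. Subtracting each subject's log factor from log AUC before fitting the model gives the same point estimate and a 90% CI that allows for variation in the factor. Set the window length in the PK Analysis Plan from the expected IgG kinetics.
2. **Item iv, full PK population.** State that this factor is not defined for subjects who came from SCIG, since they have no current pre-study IGIV dose.
3. **Primary analysis.** Keep it as planned. Flag subjects with a missed infusion, or a mg/kg change beyond weight adjustment, in the same window, and add one sensitivity analysis without them. State that dropping raised-dose subjects removes low-exposure subjects and may bias that ratio upward.
4. **Text.** The sponsor should reconcile 8.2.1 with the steady-state labels in 7.1 and 13.2.2.1. Whether and how the dose may change remains its clinical decision.

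No new data are needed. Actual mg/kg at each infusion is already derived (SAP 13.1), prior dose and interval are recorded (Protocol 7.12), and the PK Analysis Plan is to be finalised only before database lock. The cost is a little more analysis work and a slightly wider interval in the sensitivity run.
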